## HEALTH ECONOMIC EVALUATION

The net costs and benefits of the intervention compared to the control will be described and reported in accordance with the Consolidated Health Economic Evaluation Reporting Guidelines (CHEERS). [97] For each intervention arm, the probability of resource use and associated costs will be reported. Cost estimates will be presented in terms of direct costs (e.g., healthcare), indirect costs (e.g. lost productivity) and out-of-pocket costs. Unit prices for resources utilised will be sourced from the most appropriate and up-to-date source (e.g., PHARMAC). Costs will be measured in actual prices for the reference year (e.g., 2023). Where prices in 2023 are unavailable, adjustment to the actual price will be made using the published health sector specific deflator/inflators. The overall 'Program Costs' (i.e., non-research related costs associated with providing the intervention) will be deducted from the potential cost-offsets from fewer readmissions or other resource savings. Sensitivity and uncertainty (probabilistic multivariable [Monte-Carlo simulated]) analyses to account for variability in point estimates will be performed to assess the robustness of results.

The analysis will include modelling the potential opportunity cost savings from future strokes averted based on changes in risk profile (e.g., change in absolute 5-year risk of stroke or clinically relevant change in LS7 score). An incremental cost/ quality-adjusted life year (QALY) gained will also be calculated. The EQ5D is the most commonly used in economic evaluations to estimate preference-based outcome measure and will be used to calculate QALYs for the cost utility analysis.[62, 98] Threshold and willingness-to-pay analyses, illustrated using cost effectiveness acceptability curves, will be performed to assess uncertainty in the model parameters or a range of different scenarios, to explore under what conditions HWC could be cost effective and yield potential cost offsets/savings. Potential savings will be calculated using a "case-averted" approach, which estimates the direct and indirect costs savings if the use of HWC leads to annual reduction in stroke incidence. These estimates will be extrapolated to the overall New Zealand population.

## TRIAL ORGANISATIONAL STRUCTURE

The TIIPS trial host centre is The National Institute for Stroke and Applied Neurosciences, Auckland University of Technology, Auckland, New Zealand.

---

## 36. TRIAL COMMITTEES

The Steering Committee of TIIPS, consists of investigators on the grant with additional invited members. This Committee will view and comment on essential study documents and comment on major changes to the study protocol. This committee has an advisory role and due to its membership including staff from the District Health Boards, ensures liaison with stakeholders. The Committee will meet monthly (or as needed) and has the opportunity to approve all study documentation and procedures, but this does not require a mandate. The Steering Committee is responsible for the overall management of the trial including all aspects of trial design, conduct, analysis and publication, including:

- Trial design and recruitment
- Data management
- Committee coordination
- Ethics committee and Locality applications
- Initiation visits to participating centres
- Monitoring of data quality and adherence to applicable guidelines and regulations
- Statistical analysis
- Preparation of the final report and manuscript of main findings

The Operations Committee will be under the guidance of the Study Co-PI and study Project Manager, and will oversee the day-to-day management of the trial, including

- Participant consent and recruitment
- Protocol and procedures training
- Data entry and management
- Participant communication and queries
- Preparation of reports for the Steering Committee

---

## 37. STAFF TRAINING

Research assistants who will be conducting assessments will attend online and in-person training sessions on all aspects of their role, including,

- the design and aims of the TIIPS trial

- Informed consent processes, participant recruitment, and booking appointments
- Data collection and entry on REDCap
- Assessment processes, including physical, cognitive and psychological measures, and completion of individual questionnaires, cultural considerations
- Reporting of adverse events
- Regular attendance of research assistant meetings

## ETHICAL CONSIDERATIONS

The study will seek ethical approval for research in human participants through the Health and Disability Ethics Committees (HDECs) (<https://ethics.health.govt.nz/>). The processes of Informed consent and confidentiality will be informed by the National Ethical Standards for Health and Disability Research and Quality Improvement.

In addition, the study will seek institutional ethical approval from the AUT ethics committee (AUTEC) (<https://www.aut.ac.nz/research/researchethics>)

Locality Approvals will be sought for each of the District Health Boards (DHBs): Auckland, Waitemata and Counties Manukau, according to their guidelines.

Māori and Pacific cultural consultations will be conducted via the AUT Vision Mātauranga Committee and DHB Māori advisory teams.

## DATA MANAGEMENT

The data will be managed by NISAN and stored at AUT University. Physical information (i.e. paper copies) will be kept in locked cabinets in secure offices at AUT. Computerised data will be kept on secure AUT servers. No identifiable data will be stored on cloud or shared via emails. AUT University follows a rigorous process where the data is stored, retained, and disposed in an ethical manner. The information is required to be protected under the NZ Health Information Privacy Code 1994 and NZ Privacy Act 1993. Information will not be shared with any third party.

The data will be kept for a period of 10 years. This is so that we can analyse this data and report it to the participants, agencies, and communities effectively. After 10 years all information will be destroyed by the study manager by deleting records on the REDCap database and shredding the

paper copies. De-identified and aggregated data will be retained to conduct secondary analyses and for data pooling.

Although the participants will share some identifiable information, it will be stored on REDCap in an anonymised fashion and not shared outside the small research team. The participants will also be providing information about their estimated risk of having a stroke in the future. However, this information will not be linked to their identifiable information.

Data capture will be facilitated using REDCap (Research Electronic Data Capture) – a secure web-based application designed specifically for this purpose in a research study setting. REDCap provides 128-bit encryption from client to server, audit trails, easy-to-use forms with real-time field validation, ability to export to a variety of statistical packages, and security features (including user permissions). Two-factor authentication (2FA) is mandated system wide. AUT's ICT department manages and performs daily backups of the local REDCap installation, and appointed research data managers will develop, support and maintain the project's database structure and content.

Although data collection will be conducted via face-to-face manner at specified AUT clinics, data capture will be performed by Research Assistants (RA) using the web-based interface of REDCap. Each RA will have their own REDCap account and will be required to re-authenticate via Google Authenticator or email verification (presently the re-authentication window is 6.5 days). All direct identifiers will be marked accordingly in REDCap – only those users with appropriate training and permissions will be able to export these variables.

REDCap has a comprehensive user rights module that allows the ability to define user roles with specific rights to access forms and functionality and then assign users to each role. Once assigned user roles, the user can only interact with forms and records in a controlled environment. This feature protects unauthorised users from accessing identifiable participant information such as National Health Index (NHI) number, Date of birth (DoB).

Data collected and resulting publications from this study are the property of the National Institute for Stroke and Applied Neurosciences, AUT University.

## CASE REPORT FORMS

The study Case Report Form (CRF) is the primary data collection instrument for the study. All data requested on the CRFs must be recorded on REDCap. All missing data must be explained. CRFs are used to record clinical study data and are an integral part of the study and subsequent reports. CRFs must be kept current to reflect subject status at each phase during the course of the

study. The investigator will be responsible for retaining all records pertaining to the study. The CRFs for the TIIPS study as designed in REDCap are listed in Appendix C.

## VISION MATAURANGA STATEMENT FOR PROJECT

Vision Mātauranga provisions for this project will ensure that Māori have access to their spiritual realm, their language and protocols throughout the consultation, implementation and reporting phases of this project.

AUT researchers have obligations under the Treaty of Waitangi and AUT's Vision Mātauranga policies to engage with iwi in a culturally safe manner. The values outlined in the AUT Vision Mātauranga policies require all staff to foster a culturally safe environment that promotes whānau support values. All whānau of Māori decent within this study will be able to opt into or out of the Vision Mātauranga provisions.

## PUBLICATION POLICIES AND DISSEMINATION PROCESSES

This trial will be registered with <https://www.anzctr.org.au/>, (Australian New Zealand Trials Registration Number: TBA) an organisation that maintains a database of trials in progress to assist with the synthesis of controlled trials. The main results will be published as a journal article in a relevant journal as well as an internal report for NISAN.

In this context 'publication' refers to all work for intended for dissemination, as well as any poster or oral presentations of materials. The project lead refers to the person wishing to produce material for dissemination.

### **Steps to take:**

As the Principal Investigator has ultimate responsibility for all aspects of the study performance and presentations, the Project Lead needs to discuss a preliminary idea about the proposed publication with the Principal Investigator.

The Project Lead will email their idea(s) to a person responsible for circulation of the Steering Committee agenda or PA of [name] (cc'd to the Principal Investigator and Co-Directors of the ARCOS V Programme TIIPS trial) to be added to the agenda for the next Steering Committee

meeting. The email should include a brief title/description of the topic so that committee members unable to attend the meeting can comment.

For programme related works, The Project Lead will discuss the nominated publication(s) with Trial Steering Committee to agree the publication is in keeping with the key objectives of the programme, nominate junior researchers who they recommend be contributors to the publication and, ensure potential conflict with existing work are managed. The decision of the Programme Co-Directors will be entered in the minutes.

The proposed idea is to be discussed at the next Steering Committee meeting. At this stage the core individuals to contribute to the paper/presentation are to be identified (this is the *Writing Committee* for that particular work) and the most suitable forum for the work is to be discussed.

Authorship will include those on the writing committee as well as any other members of the Steering committee who make a significant contribution. In the case of extensive multiple authorship being appropriate, the Writing Committee will be named authors and others will be represented in an agreed collective title

All decisions relating to proposed dissemination ideas are to be minuted. The minutes should include an invitation to any Steering Committee members who were unable to attend the meeting to contact the primary author taking responsibility for the work before the next Steering Committee meeting if they also wish to contribute.

All project team members will be advised of the proposed publication, and can at this point indicate if they would like to contribute.

Once the publication is nearing completion, and has had input from all Writing Committee members, it is then to be circulated with the agenda for the next Steering Committee meeting before submission.

At this stage, discussion should pertain to ensure that the Authorship is appropriate and the targeted forum for the publication is the most appropriate (rather than manuscript content). At the end of this discussion, the decision of the Steering Committee should be minuted.

The Steering Committee should be informed of any editorial decisions made through presentation at the Steering Committee meeting. This includes acceptances as well as rejections, and in the case of rejections should contribute to any decisions about further submissions. All such developments should be minuted.

If the work is restricted by a tight timeframe (e.g. conference abstract submission deadline before the next steering committee meeting), the work may be approved for submission by the

Principal Investigator and Co-Directors and the Steering Committee members informed of the decision.

# APPENDICES

## 38. APPENDIX A: PHYSICAL MEASURES AND EQUIPMENT

### *Requirements for face-to-face visit*

The Participant File with information and consent form.

MoCA hardcopy for cognitive screening.

Tablet or laptop within REDcap database open to 'baseline assessment – physical measurements' (can be used offline if no internet)

Completion of questionnaires in REDCap.

Reminder sheet about blinding of the Research Assistants so that participants do not disclose if they are in the HWC group.

The following will occur at each visit:

Any questions regarding the information sheet or consent form will be addressed, ensuring that the participant received an electronic copy of the consent form to keep and reassured that they can withdraw at any time.

Before the baseline assessment the Research Assistant should review the completed online questionnaires. This will confirm eligibility in terms of medical history before completing further eligibility checks.

The first eligibility check will be the physical measurement of blood pressure (See below under PHYSICAL MEASUREMENTS). If participants have met this criterion, the assessment will continue. The clinical testing will confirm how many biomedical items are in the unhealthy range.

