## PARTICIPANT RECRUITMENT

### 12. INCLUSION CRITERIA

1. People aged between 18 years to 75 years diagnosed with TIA or first-ever minor stroke (excluding subarachnoid haemorrhage (SAH)) (National Institutes of Health Stroke Scale (NIHSS) score  $\leq$  4) and/or modified Rankin Scale (mRS) score 0-2 at discharge [1] in the past 6 weeks

2. Admitted to one of the three Auckland based hospitals or identified via primary care for minor stroke or TIA
3. Who can converse in English
4. Provides written informed consent
5. Exclusion criteria
6. History of major stroke or myocardial infarction (verified through Clinical Portal medical records)
7. Planned carotid endarterectomy
8. Life-threatening conditions with a life-expectancy <5 years
9. Current (in the past year) significant clinical depression/anxiety (Hospital Anxiety and Depression questionnaire (HADS)  $\leq 11$  in either or both the depression and anxiety domains) (either in clinical records or at screening) OR psychiatric conditions (based on medical records),
10. History (past year) of alcohol or drug/substance abuse
11. Dependent on others (living in a rest-home/care facility)
12. Significant cognitive impairment or pre-existing diagnosis of dementia e.g. ACE-R  $\leq 82$  (from clinical records), or at screening (MoCA (<26))
13. Participation in another RCT

The majority of the inclusion and exclusion criteria will be determined by means of medical record/clinical portal screening, completed by hospital based research staff. If all the relevant information is not available, the initial section of the Baseline assessment will allow further screening to check for remaining criteria (e.g. cognitive impairment or abnormal mood). Exclusion due to significant anxiety and depression [58, 59] or cognitive impairment [60] are necessary in order to recruit participants who will be able to engage effectively with the study over a period of 12 months.

---

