### *Confirmation of non-medical inclusion & exclusion criteria:*

Participants that have proceeded to this stage will have met the cut-off for blood pressure score.

Following this, the Research Assistant will use a hard copy of the MoCA© and enter results directly into the REDCap form. This will calculate total score. If participant scores <26 they will need to be excluded. The Research Assistant performing the MoCA© should complete the online MoCA© Training and Certification Program at <https://www.mocatest.org/>.

If the inclusion criteria are met, the participant will proceed to complete the Hospital Anxiety and Depression (HADS) questionnaire. If the score for HADS is greater than 11 in either the Anxiety or Depression domains, the participant is ineligible to continue.

If participants are ineligible at this stage they will be notified of not meeting the study requirements and thanked for their interest in the study. They should be offered reimbursement for their time, if requested, in line with local ethics approvals.

The RAs conducting the assessments will be provided with the study Manual of Procedures, outlining all the day to day processes for conducting the study, safety information, contact details of senior study staff, as well as a field manual for easy reference. They will also be provided with iPads for data entry, mobile phones and stationary for data collection and record keeping.

---

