1.20. History (past year) of alcohol or drug/substance abuse  Yes  No

1.21. Dependent on others (living in a rest-home/care facility)  Yes  No

1.22. Significant cognitive impairment or pre-existing diagnosis of dementia e.g., ACE-R  $\leq$  82 (from clinical records), or at screening (MoCA) (If unknown, check unknown, to be completed by RA at Baseline screening).  Yes  No  Unknown

If YES to any of the above, this participant is not eligible. Stop here.

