**Section 15. LS7 Questionnaire**

**Part A: Blood Pressure**

15A.1. Systolic blood pressure (mm Hg) Reading 1

\_\_\_\_\_

15A.2. Diastolic blood pressure (mm Hg) Reading 1

\_\_\_\_\_

15A.3. Systolic blood pressure (mm Hg) Reading 2

\_\_\_\_\_

15A.4. Diastolic blood pressure (mm Hg) Reading 2

\_\_\_\_\_

15A.5. Systolic blood pressure (mm Hg) Reading 3

\_\_\_\_\_

15A.6. Diastolic blood pressure (mm Hg) Reading 3

\_\_\_\_\_

15A.7. Average Systolic blood pressure (mm Hg)

\_\_\_\_\_

If the average systolic blood pressure is less than 130, please stop here. Participant is not eligible.

15A.8. Average Diastolic blood pressure (mm Hg)

\_\_\_\_\_

15A.9. LS7 BP Score

\_\_\_\_\_

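### Blood pressure is an eligibility gate in Appendix A and on Form B (average SBP below 130 is ineligible) but is absent from the section 12 criteria, and the same stop line reappears on follow-up Form F

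*Protocol*

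**What the plan says.** **Main text.** Section 12 lists the criteria, opening with "People aged between 18 years to 75 years diagnosed with TIA or first-ever minor stroke". The rest cover severity, site, language, consent, vascular history, planned surgery, life expectancy, mood, substance abuse, dependency, cognition and participation in another trial. None concerns blood pressure. The section adds that "The majority of the inclusion and exclusion criteria will be determined by means of medical record/clinical portal screening" and, where information is lacking, that "the initial section of the Baseline assessment will allow further screening to check for remaining criteria (e.g. cognitive impairment or abnormal mood").

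**Form B, Section 1.** The screening checklist (items 1.1 to 1.22) closes its exclusion list with "If YES to any of the above, this participant is not eligible. Stop here". It has no blood pressure item.

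**Appendix A.** Under the requirements for the face-to-face visit: "The first eligibility check will be the physical measurement of blood pressure", then "If participants have met this criterion, the assessment will continue". Under the confirmation of non-medical criteria: "Participants that have proceeded to this stage will have met the cut-off for blood pressure score". Neither place gives a number. The blood pressure subsection of Appendix A gives only the high readings that prompt medical referral.

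**Form B, Section 15 Part A**, after item 15A.7 (average systolic pressure): "If the average systolic blood pressure is less than 130, please stop here. Participant is not eligible". **Form F**, used at 3, 6, 9 and 12 months, carries the same line after the same item.

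**Primary endpoint** (sections 10 and 30): the between-group difference in mean change in SBP from baseline to 6 months.

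**The concern.** Eligibility must have one answer for each patient, and here it depends on which page the research assistant follows. If section 12 governs, Form B turns away eligible people. If Form B governs, anyone enrolled on section 12 alone with average SBP below 130 is what the protocol violations section gives as an example of a violation: an ineligible participant included by mistake.

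The variable makes this more than a clerical matter. A cut-off on baseline SBP determines:

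- how much room SBP has to fall;
- how much both arms will drift down through regression to the mean, since the qualifying readings are also the baseline;
- whether anyone can start in the ideal LS7 blood pressure category, which requires SBP below 120;
- to whom the result applies.

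The planning inputs (6 mm Hg, SD 20) come from a previous coaching trial that is not described as restricted to SBP of 130 or more.

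The Form F repeat raises a separate problem. At follow-up a low SBP is an outcome, possibly a good one, and an instruction to stop there would make missing data depend on it.

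**Working it through.** The plan states no figure on this point, so there is none to reproduce. The check is a comparison of text, followed by an illustration of size.

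**Step 1. One patient, four places.** Take a 60-year-old with TIA who meets everything in section 12 and has average SBP of 125.

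| Place | Result |
|---|---|
| Section 12 | Eligible; no blood pressure criterion |
| Form B, Section 1 | Passes; no blood pressure item |
| Appendix A | Must pass a blood pressure criterion; no value, and the later reference to a score does not say whether SBP or the LS7 blood pressure score is meant |
| Form B, after 15A.7 | Not eligible (125 < 130) |

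The first two and the last cannot all be right. The third cannot be applied without the number from the form.

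**Step 2. Form F.** The three systolic and three diastolic readings and the average SBP come before the stop line. After it come the average diastolic item, the LS7 blood pressure score, cholesterol, glucose, BMI, smoking, diet, activity, total LS7, the Stroke Riskometer and health service use. At 6 months the line would therefore leave the primary outcome recorded. It would lose the LS7 total, the first secondary endpoint in section 31, and the later items in participants with SBP below 130 only. If coaching lowers SBP, more of these would be in the coaching arm.

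**Step 3. Size, illustration only.** The protocol gives no baseline SBP for this population. Assume SBP is normal with mean μ and SD σ. Then P(SBP < 130) = Φ((130 − μ)/σ). With σ = 17 (assumed):

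- μ = 130: Φ(0) = 50%
- μ = 135: Φ(−0.294) = 38%
- μ = 140: Φ(−0.588) = 28%

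The only SBP distributions in the protocol (section 4, Finnish men without stroke, by LS7 category) give:

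- 138.2, SD 16.6: Φ(−0.494) = 31%
- 132.0, SD 16.5: Φ(−0.121) = 45%
- 118.6, SD 12.4: Φ(0.919) = 82%

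For the first two, enrolling 360 would need about 360/(1 − 0.311) = 523 and 360/(1 − 0.452) = 657 otherwise eligible people.

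The gate would also change who is enrolled. With α = (130 − μ)/σ and λ = φ(α)/(1 − Φ(α)), the enrolled mean is μ + σλ and the SD is σ√(1 + αλ − λ²). For 138.2 (SD 16.6) this gives 146.7 (SD 11.6). For 132.0 (SD 16.5) it gives 143.9 (SD 10.3).

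**Step 4. Order.** Appendix A measures blood pressure before MoCA and HADS. Form B places it in Section 15, after both and after item 8.18 has asked whether all screening questions are complete.

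**The case against.** The best defence is that the rules add up rather than conflict. Section 12 foresees further screening at baseline, section 29 says the first part of that visit settles full eligibility, and everyone passes through Form B. The form also carries other screens that section 12 omits: staying in Auckland for 12 months, adequate hearing, and pre-event mRS above 2. On this view section 12 is merely incomplete.

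This may well describe what was intended, but it does not remove the conflict. Section 12 is the stated list of criteria, and what it leaves to baseline is the checking of remaining criteria from that list, with cognition and mood as its examples. The other extra screens at least sit in the Form B Section 1 checklist; the blood pressure rule does not. The flowchart and CONSORT chart are not shown and might mention blood pressure, but that would not repair section 12.

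Several stronger readings are tempting and are not supported:

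- **That Appendix A itself sets 130.** It gives no value; the number is only on Forms B and F.
- **That a quarter to a half of patients are known to be affected.** The 28% to 50% range rests on an assumed mean and SD, and the Finnish figures run from 31% to 82%.
- **That patients have already been enrolled under two rules.** The document reads as pre-start: ethics approval is still to be sought, the safety committee is to be appointed and the registration number is pending.
- **That Form F would delete the primary outcome in the best responders.** Average SBP is entered before the line. The line may also be a copying error: Form F likewise repeats the MoCA ineligibility note, though without the stop instruction printed with it on Form B.
- **That the gate biases the treatment comparison.** It acts before randomisation, so regression to the mean is expected alike in both arms.
- **That the form order is a serious conflict.** Section numbers on a form do not fix the sequence of a visit, so this is minor.

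**Conclusion.** The contradiction stands on the text alone and needs no assumption. Section 12 and the Form B checklist admit patients at any SBP, Appendix A requires a blood pressure criterion it does not define, and Form B item 15A.7 excludes average SBP below 130. Because the rule acts on the baseline value of the primary endpoint, it should be settled before the first participant is screened. Who was randomised cannot be corrected afterwards.

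The share of patients whose status changes is unknown. The percentages above show only that it could be large under plausible-looking inputs. The Form F line is a second defect: taken literally, it would lose the later secondary items selectively at 6 months. The documents do not show which eligibility rule the sponsor intends, and this review does not choose one.

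**What to change.** 1. Reconcile section 12, both Appendix A statements and Form B item 15A.7 so that one rule, whichever the sponsor intends, appears identically in all of them. Either state the measure and value everywhere (for example, whether it is the average of the three systolic readings) or remove the gate everywhere.
2. Delete the eligibility stop line from Form F in either case.
3. If a cut-off is kept, count those who fail it in the CONSORT chart, and state whether the 6 mm Hg and SD 20 planning inputs apply to the restricted population.
4. If anyone has been enrolled by the time this is corrected, report how many were handled under each rule.
5. Minor: if the gate stays, align the Form B order with Appendix A, which puts blood pressure first.

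The cost is small: short edits to section 12, Appendix A and Forms B and F, made in one amendment with the matching REDCap change. No new data or analysis is needed.
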